2.1.4 Safety endpoints

The safety analyses will be based on the reported adverse events (AEs) and other safety information, such as clinical laboratory data, vital signs, and tanner stage assessment.

Observation period

The period of safety observation starts from the time when the patient gives informed consent and is divided into the following periods:

- The PRE-TREATMENT period: defined as the time from the signed informed consent up to the first dose of IMP injection in the study;
- The OLDFI treatment-emergent adverse event (TEAE) period: defined as the time from the first OLDFI IMP injection up to the day of last OLDFI IMP injection + 70 days (10 weeks) as residual effect of alirocumab is expected until 10 weeks after discontinuation. For patients entering in the OLE, the OLDFI TEAE period will be truncated at the day before the first OLE IMP injection in the extension period;

The OLDFI TEAE period will include:

- The OLDFI TREATMENT period: defined as the time from the first OLDFI IMP injection up to the day of last OLDFI IMP injection + 21 days (for Cohorts 1 & 2) or + 35 days (for Cohort 3 & 4) . For patients entering in the OLE, the OLDFI treatment period will truncated at the day before the first OLE IMP injection in the extension period
- The OLDFI POST-TREATMENT period defined as the time starting the day after the end of OLDFI TEAE period. For patients entering in the OLE, the OLDFI POST-TREATMENT period will be truncated at the day before the first OLE IMP injection in the extension period;
- The OLDFI/OLE combined TEAE period: defined as the time from the first OLDFI IMP injection up to the day of last OLE IMP injection (or to last OLDFI IMP injection for patients not entering into the extension phase) + 70 days ;

The OLDFI/OLE combined TEAE period will include:

- The OLDFI/OLE combined TREATMENT period defined as the time from the first OLDFI IMP injection up to the day of last OLE IMP injection (or to last OLDFI IMP injection for patients not entering into the extension phase) + 21 days (for Cohorts 1 to 2) or + 35 days (for Cohorts 3 & 4). For patients from Cohort 3 who switched to selected Phase 3 doses, the OLDFI/OLE combined TREATMENT period is defined as

the time from the first OLDFI IMP injection up to the day of last OLE IMP injection
+ 21 days.

- The OLDFI/OLE combined POST-TREATMENT period defined as the time starting the day after the end of the OLDFI/OLE combined TEAE period.

The OLDFI on-study observation period is defined as the time from the day of first OLDFI IMP injection until the last protocol planned OLDFI visit of the patient. The last protocol planned OLDFI visit is defined as the final follow-up visit if done, else 10 weeks after last OLDFI IMP injection.

The OLDFI/OLE combined on-study observation period is defined as the time from the first OLDFI IMP injection until the last protocol planned visit of the patient. The last protocol planned visit is the final follow-up visit in OLDFI period for patients not proceeding into OLE period or in OLE period for patients proceeding into OLE period.

2.1.4.1 Adverse events variables

Adverse events (including serious adverse events (SAEs) and adverse events of special interest (AESIs)) are recorded from the time of signed informed consent until the end of study. All AEs diagnosed by the Investigator will be reported and described.

All AEs will be coded to a “lowest level term (LLT)”, “preferred term (PT)”, “high level term (HLT)”, “high level group term (HLGT)” and associated primary “system organ class (SOC)” using the version of MedDRA currently in effect at Sanofi at the time of database lock.

Adverse event observation period

- Pre-treatment AEs are AEs that developed or worsened or became serious during the pre-treatment period.
- OLDFI treatment-emergent adverse events are AEs that developed or worsened or became serious during the OLDFI TEAE period.
- OLDFI post-treatment AEs are AEs that developed or worsened or became serious during the OLDFI post-treatment period.
- OLDFI/OLE combined treatment-emergent adverse events are AEs developed or worsened or became serious during the OLDFI/OLE combined TEAE period.
- OLDFI/OLE combined post-treatment AEs are AEs that developed or worsened or became serious during the OLDFI/OLE combined post-treatment period.

Groupings of Adverse events

Grouping of Adverse events include the following:

- Local injection site reactions (AESIs or not), selected using e-CRF specific tick box on the adverse event page

- Allergic events
 - General allergic events (AESIs or not), selected using SMQ “hypersensitivity” (broad and narrow) excluding the following preferred terms linked to local injection site reactions (“infusion site dermatitis”, “infusion site hypersensitivity”, “infusion site rash”, “infusion site urticaria”, “injection site dermatitis”, “injection site hypersensitivity”, “injection site rash”, “injection site urticaria”, and “injection site vasculitis”)
 - General allergic events (AESIs or not) and local allergic reactions at IMP injection site will be described. This selection will be based on the above selection for general allergic event and on the following selection of PT from the symptoms complementary form for local injection site reaction ("Injection site dermatitis", "Injection site hypersensitivity", "Injection site oedema", "Injection site rash", "Injection site urticaria", "Injection site eczema", "Injection site vasculitis", "Injection site swelling", "Infusion site dermatitis", "Infusion site hypersensitivity", "Infusion site oedema", "Infusion site rash", "Infusion site urticaria", "Infusion site swelling")
- ALT >3 ULN, selected using laboratory data
- Neurologic events (AESIs or not), selected using a CMQ based on SMQs “demyelination” (broad and narrow), “peripheral neuropathy” (broad and narrow), and “Guillain-Barre syndrome” (broad and narrow) excluding the following preferred terms “acute respiratory distress syndrome”, “asthenia”, “respiratory arrest” and “respiratory failure” and including selected PTs from SMQ “optic nerve disorders” (see [Table 6](#) for the list of terms)
- Neurocognitive events:
 - Selected using a CMQ, based on the following 5 HLG Ts: “deliria (including confusion)”, “cognitive and attention disorders and disturbances”, “dementia and amnestic conditions”, “disturbances in thinking and perception”, and “mental impairment disorders”
 - A second grouping of terms for neurocognitive events was defined based on Regulatory Agency request (see [Table 7](#) for the list of terms)
- Symptomatic overdose of IMP, selected using appropriate MedDRA codes and the tick boxes “Overdose of Alirocumab” and “Symptomatic Overdose” in the overdose adverse event form
- Pregnancy (including male patient’s partner) selected using appropriate MedDRA codes

Analyses of allergic and neurologic events will also be provided using the tick box on the e-CRF AE page as a second approach.

In addition the additional grouping of events will be provided:

- Hepatic disorder events using SMQ “Hepatic disorder”
- Diabetes mellitus or diabetic complications using HLT “diabetes complications” (including PTs pertaining to the secondary SOC included in the HLT), HLT “diabetes

mellitus”, and HLT “carbohydrate tolerance analyses (incl diabetes)” excluding PTs “blood glucose decreased” and “Glycosylated haemoglobin decreased” and including the PTs “hyperglycaemia”, “Hyperglycaemic unconsciousness” and “Hyperglycaemic seizure” from the HLT “Hyperglycaemic conditions NEC”

- Cataract using HLT “Cataract conditions”

2.1.4.2 Deaths

The deaths observation period are per the observation periods defined above.

- Death on-study during OLDFI period: deaths occurring during the OLDFI on-study observation period,
- Death on-treatment during OLDFI period: deaths occurring during the OLDFI TEAE period,
- Death on-study during the OLDFI/OLE combined period: deaths occurring during the OLDFI/OLE combined observation period,
- Death on-treatment during the OLDFI/OLE combined treatment periods: deaths occurring during the OLDFI/OLE combined TEAE period,
- Death post-study: deaths occurring after the last planned protocol visit.

2.1.4.3 Laboratory safety variables

Clinical laboratory data consist of blood analysis, including hematology and clinical chemistry, fat soluble vitamins, gonadal hormones, pituitary hormones, and adrenal gland hormones. Clinical laboratory values will be analyzed into international units. Clinical laboratory values converted into conventional (US) units will be also available in the database. Analyses can be provided upon request. Unless otherwise specified below, blood samples for clinical laboratories were to be collected during:

- Screening at Visit 1 (up to Week -6),
- The OLDFI period at Visit 2 (Week 0), Visit 4 (Week 4), Visit 6 (Week 8) or early termination, and during the follow-up visit [Visit 8 (Week 14 for Cohort 3 or Week 16 for Cohorts 1& 2)] (for pregnancy test or in case of abnormality at the visit 6 in hematology and chemistry parameters),
- The OLE period at Visit 8 (Week 16 for Cohorts 1& 2 or Week 14 for Cohort 3)], Visit 11 (Week 28 for Cohorts 1& 2 or Week 26 for Cohort 3 or Week 24 for Cohort 4), Visit 13 (Week 52 for Cohorts 1& 2 or Week 50 for Cohort 3 or Week 48/ end of OLE period for Cohort 4), Visits 15, 17, 19 (every 24 weeks for Cohorts 1 to 3) and Visit 20 (Week 130/ end of OLE period for Cohorts 1 to 3 or early termination during OLE period for all cohorts).

The laboratory parameters (excluding those considered as efficacy parameters) will be classified as follows:

- Hematology
 - **Red blood cells and platelets:** hemoglobin, hematocrit, red blood cell count, platelet count;
 - **White blood cells:** white blood cell count, neutrophils, lymphocytes, monocytes, basophils, eosinophils.
- Clinical chemistry
 - **Metabolism:** glucose, total protein, albumin, creatine phosphokinase (CPK);
 - **Electrolytes:** sodium, potassium, chloride, calcium, phosphorus, bicarbonate;
 - **Renal function:** creatinine, eGFR, blood urea nitrogen, uric acid;
 - **Liver function:** alanine aminotransferase (ALT), aspartate aminotransferase (AST), alkaline phosphatase (ALP), gamma glutamyl transferase (γ GT), lactate hydrogenase (LDH), total bilirubin, and in case of total bilirubin values above the normal range, must include conjugated and non-conjugated bilirubin (used for describing individual cases only).
- **Adrenal gland hormones:** cortisol (with reflexive ACTH levels if cortisol <LLN) and dehydroepiandrosterone sulfate (DHEAS).
- **Pituitary hormones:** luteinizing hormone (LH) and follicle-stimulating hormone (FSH).
- **Gonadal hormones:** testosterone (male) and estradiol (females).
- **Fat soluble vitamins:** A (retinol), D (25 hydroxy vitamin D), E (alpha-tocopherol), and K (phylloquinone).
- **Serum pregnancy test:** blood test at screening visit and local urine pregnancy test for all other tests.

Technical formulas are described in [Section 2.5.1](#).

2.1.4.4 Vital signs variables

Vital Signs parameters include Weight, Heart Rate (HR), Systolic and Diastolic Blood Pressure (SBP and DBP) in sitting position and were to be measured during:

- Screening at Visit 1 (up to Week -6),
- The OLDFI period at Visit 2 (Week 0), Visit 4 (Week 4), Visit 6 (Week 8) for Cohorts 1 to 4 or early termination (for Cohorts 1 to 3), and Visit 8 (follow-up visit for Cohorts 1 to 3, Week 14 for Cohort 3 or Week 16 for Cohorts 1& 2, and Week 12 or early termination for Cohort 4,

- The OLE period at Visit 8 (Week 16 for Cohorts 1& 2 or Week 14 for Cohort 3, or Week 12 for Cohort 4), Visit 12 (Week 40 for Cohorts 1& 2 or Week 38 for Cohort 3 or Week 36 for Cohort 4), Visit 13 (Week 48/ end of OLE period for Cohort 4), Visits 14, 16, 18 (every 24 weeks for Cohorts 1 to 3) and Visit 20 (Week 130/ end of OLE period for Cohorts 1 to 3 or early termination during OLE period for all cohorts).

2.1.4.5 *Electrocardiogram variables*

Not Applicable.

2.1.4.6 *Tanner stages measurement*

Tanner stages measurement include assessments of boys—development of external genitalia, girls—breast development, boys/girls—pubic hair, performed if possible by the same investigator/designee trained to assess pubertal development, during:

- Screening at Visit 1 (up to Week -6)
- The OLDFI period at Visit 8 (follow-up visit for Cohorts 1 to 3, Week 14 for Cohort 3 or Week 16 for Cohorts 1& 2) or Week 12 or early termination for Cohort 4,
- The OLE period at Visit 8 (Week 16 for Cohorts 1& 2 or Week 14 for Cohort 3 or Week 12 or early termination for Cohort 4), Visit 12 (Week 40 for Cohorts 1& 2 or Week 38 for Cohort 3 or Week 36 for Cohort 4), Visit 13 (Week 48/ end of OLE period for Cohort 4), Visits 14, 16, 18 (every 24 weeks) and Visit 20 (Week 130/ end of OLE period for Cohorts 1 to 3 or early termination during OLE period for all cohorts).

2.1.4.7 *Other endpoints*

Other endpoints listed below are defined using same definitions and rules as for calculated LDL-C, when applicable (see [Section 2.1.3](#)) and include:

- The proportion of patients with two consecutive results, spaced out by at least 21 days, of LDL-C <50 mg/dL (<1.30 mmol/L) and (calculated LDL-C <25 mg/dL ie, <0.65 mmol/L) respectively during OLDFI period or the OLDFI/OLE combined period
- The time to the first LDL-C <50 mg/dL (respectively, calculated LDL-C <25 mg/dL) for these patients within the relevant analysis period specified above.

2.1.4.8 *Anti-alirocumab antibodies variables*

Anti-alirocumab antibodies (ADA) are assessed:

- At baseline (see [Section 2.1.1](#) for definition)
- During the OLDFI period at Week 8 or early termination and during follow-up (Week 16 for Cohorts 1& 2 or Week 14 for Cohort 3) and Week 12 for Cohort 4

- During the OLE period at Visit 8 (Week 16 for Cohorts 1& 2 or Week 14 for Cohort 3 or Week 12 for Cohort 4), Visit 11 (Week 28 for Cohorts 1& 2 or Week 26 for Cohort 3 or Week 24 for Cohort 4), Visit 13 (Week 52 for Cohorts 1& 2 or Week 50 for Cohort 3 or Week 48/ end of OLE period for Cohort 4), Visits 15, 17, 19 (every 24 weeks) and Visit 20 (Week 130/ end of OLE period for Cohorts 1 to 3 or early termination during OLE period for all cohorts).

ADA measurements will be assigned to the same analysis windows as defined for efficacy endpoints ([Table 3](#) and [Table 4](#)).

The following variables will be described for both OLDFI period and the OLDFI/OLE combined period:

- ADA response (Positive or Negative).

For ADA positive:

- Titer levels
- Neutralizing status (Positive or Negative)
- Pre-existing positive ADA defined as patients with positive ADA response at baseline with less than 4-fold increase in titer in the post-baseline period
- Treatment-emergent positive ADA response defined as
 - Patients with no ADA positive response at baseline but with any positive response in the post-baseline period (for OLDFI period: up to follow-up visit, for the OLDFI/OLE combined period: up to end of OLE period); OR
 - Patients with a positive ADA response at baseline and at least a 4-fold increase in titer in the post-baseline period (for OLDFI period: up to follow-up visit, for the OLDFI/OLE combined period: up to end of OLE period).
 - For treatment-emergent positive ADA, the following categories for ADA duration will be applied for the analysis performed on the OLDFI/OLE combined period:
 - A persistent positive response is a treatment-emergent ADA positive response detected in at least 2 consecutive post-baseline samples separated by at least a 12-week period
 - An indeterminate duration positive response is defined as ADA present only at the last sampling time point
 - A transient positive response is defined as any treatment-emergent positive ADA response that is neither considered persistent nor indeterminate

In addition, potential ADA samples to be collected in case of ADA titer ≥ 240 at the last measurement for patients not entering to the OLE phase, or for patients proceeding into OLE phase but not entering into the Phase 3 study will be listed.

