	
Absolute change in Apo B, non-HDL-C, Total-C, Lp(a), TG, HDL-C, Apo A-1, ratio Apo B/Apo A-1 from baseline to Week 8. 
Safety endpoint(s):
 
Safety parameters: adverse events (AE)s, serious AEs (SAE), AESIs, laboratory data, vital signs, body weight, height, and Tanner stage assessed throughout the study. 
Other endpoint(s):
 
Anti- alirocumab antibodies assessed throughout the study.Alirocumab and PCSK9 concentrations assessed throughout the study.To evaluate the long-term efficacy and safety of alirocumab during the extension phase.

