9.2.3 Safety endpoints

The safety endpoints will be adverse events, serious adverse events, adverse events of special interest, laboratory data, vital signs, Tanner stage assessment, body weight, and height assessed throughout the study.

9.2.3.1 *Observation period*

The observation of safety data will be as follows:

- Pretreatment period: The Pretreatment observation period is defined from the signed informed consent up to the first dose of IMP.
- Treatment emergent adverse event (TEAE) period: The TEAE observation period is defined as the time from the first dose of IMP to the last dose of IMP injection +70 days

(10 weeks) as residual effect of alirocumab is possible until 10 weeks after the stop of treatment IMP injection.

- Post-treatment period: The post-treatment observation period is defined as the time starting the day after the end of the TEAE period up to the end of the study (see definition in [Section 6.2.2](#)).

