9.2.4 Vital signs measurement

Vital signs include: heart rate, systolic and diastolic BP in sitting position.

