- Cohort 4 will receive second alirocumab allocation and administration for OLE phase.
- Check of stability of background LMT.
- IVRS/IWRS contact to get treatment kit number for 1 kit resupply.
- Obtain fasting blood sample for:
 - Lipids: total-C, calculated LDL-C, HDL-C, TG, non-HDL-C, Apo B, Apo A-1, ratio Apo B/Apo A-1, and Lp(a) for Cohorts 1 to 3.
 - Lipids: total-C, calculated LDL-C, HDL-C, TG, non-HDL-C for Cohort 4.
 - Liver panel (ALT, AST, ALP, and total bilirubin),
 - Hematology: red blood cell count including hematocrit, hemoglobin, WBC count with differential count and platelets,
 - Chemistry: glucose, sodium, potassium, chloride, bicarbonate, calcium, phosphorous, urea nitrogen, creatinine, uric acid, total protein, LDH, albumin, and γ GT,
 - CPK,
 - Anti-alirocumab antibodies,
 - Adrenal gland hormones: cortisol (with reflexive ACTH levels if cortisol <LLN), dehydroepiandrosterone sulfate (DHEAS),
 - Gonadal and pituitary hormones: testosterone (male) and estradiol (female), luteinizing hormone (LH), follicle-stimulating hormone (FSH),
 - Fat soluble vitamins: retinol (vitamin A), 25hydroxy-vitamin D (vitamin D), alpha-tocopherol (vitamin E), phylloquinone (vitamin K).
- Reminders:
 - An appointment will be given for the next study site visit,
 - Remind patient to be in fasting conditions (ie, overnight, at least 8 hours fast and refrain from smoking) for next study site visit. Also, alcohol consumption within 48 hours and intense physical exercise within 24 hours preceding the next study site visit are discouraged,
 - Patient to bring the diary, and used and unused kits at the next study site visit.

10.1.4.5 Visits 12, 14, 16, 18 (every 24 weeks)/ Visit 12 only for Cohort 4

- Collect AEs.
- Record concomitant medication.
- Perform physical examination.
- Get body weight and height measurements.
- Get Tanner stage measurement by the same investigator/designee at each visit if possible.

- Take vital signs including HR and BP.
- Urine pregnancy test (females who have experienced menarche only).
- Review patient's diet. Patient should be on a diet in accordance with the American Academy of Pediatrics guidelines (1) or equivalent.
- If the prefilled syringe becomes available: Data collection on alirocumab administration and alirocumab compliance check by review of diary and treatment kit accountability.
- Check of stability of background LMT.
- IVRS/IWRS contact to get treatment kit number for 1 kit resupply.

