 - Rosuvastatin daily dose in mg (<5, 5, 10, 20, >20, Other);
 - Simvastatin daily dose in mg (<10, 10, 20, 40, >40, Other);
 - Pravastatin daily dose in mg (<10, 10, 20, 40, >40, Other);
 - Lovastatin daily dose in mg (<10, 10, 20, 40, >40, Other);
 - Fluvastatin daily dose in mg (<20, 20, 40, 80, >80, Other);
 - Pitavastatin (at any dose);
- Any LMT other than statins
 - Any LMT other than nutraceuticals (by chemical class and drug name) including fenofibrate and ezetimibe or other non-Statin LMT;
 - Nutraceuticals (Omega 3 fatty acids (<1000mg/day), Phytosterols, Psyllium/plantago, Policosanol, Other nutraceuticals);

Other baseline characteristics

Other baseline characteristics include body mass index (BMI) in kg/m² (quantitative and qualitative variable using BMI percentiles defined according to age for boys and girls: <P5: Underweight, \geq P5 to <P85: Healthy weight, \geq P85 to <P95: Overweight and \geq P95: Obesity using the World Health Organization (WHO) growth reference 5-19 years (1, 2, 3), smoking status and alcohol habits.

Efficacy lipid parameters (quantitative variables for all efficacy parameters and the following qualitative variables) will be also summarized at baseline (see definition in [Section 2.1.1](#)):

- Calculated LDL-C: <130, \geq 130 to <160, \geq 160 to <190, \geq 190mg/dL, ie, <3.37, \geq 3.37 to <4.14, \geq 4.14 to <4.91, \geq 4.91 mmol/L;
- HDL-C: <40, \geq 40 mg/dL, ie <1.04, \geq 1.04 mmol/L;
- Non-HDL-C: <160, \geq 160 to <190, \geq 190 to <220, \geq 220 mg/dL (ie, <4.14, \geq 4.14 to <4.91, \geq 4.91 to 5.69, \geq 5.69 mmol/L);
- Fasting TGs: <150, \geq 150 to <200, \geq 200 mg/dL, category \geq 150 mg/dL (mixed dyslipidaemia) will be also displayed, ie, <1.7, \geq 1.7 to <2.3, \geq 2.3 mmol/L;
- Lp(a): <30, \geq 30 to <50, \geq 50 mg/dL, category \geq 30 mg/dL will be also displayed, ie, <0.3, \geq 0.3 to <0.5, \geq 0.5 g/L;
- Apo B: <75, \geq 75 to <90, \geq 90 mg/dL (ie, <0.75, \geq 0.75 to <0.9, \geq 0.9 g/L).

Any technical details related to computation, dates, and imputation for missing dates are described in [Section 2.5](#).

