2.4.5.4 Analyses of vital sign variables

The summary statistics (including number, mean, median, Q1, Q3, SD, minimum and maximum) of all vital signs variables in sitting position (raw values and changes from baseline) will be calculated for each visit or study assessment (baseline, each post-baseline value of the treatment period, last on-treatment, worst on-treatment value and follow-up visit).

Vital signs without position filled in will only be used for the PCSA analysis described below.

The incidence of PCSAs at any time during the TEAE period will be summarized.

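### Height is a protocol safety endpoint with no post-baseline summary in the SAP, and weight is summarised without age and sex standardisation, so the planned outputs will not describe growth

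*SAP*

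**What the plan says.** The protocol lists the safety endpoints in two places. Section 9.2.3 names "laboratory data, vital signs, Tanner stage assessment, body weight, and height assessed throughout the study", and the synopsis names "laboratory data, vital signs, body weight, height, and Tanner stage assessed throughout the study". Both keep height and body weight apart from vital signs, which section 9.2.4 defines narrowly: "Vital signs include: heart rate, systolic and diastolic BP in sitting position". Section 10.1.4 repeats the measurement during the extension ("Get body weight and height measurements"), and section 10 requires height to be measured, not self-reported. Section 11.4 leaves the extension analyses to the SAP.

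The SAP describes its safety data, beyond adverse events, with an open list, "such as clinical laboratory data, vital signs, and tanner stage assessment" (section 2.1.4). Section 2.1.4.4 then says "Vital Signs parameters include Weight, Heart Rate (HR), Systolic and Diastolic Blood Pressure (SBP and DBP) in sitting position". Section 2.4.5.4 gives the analysis: summary statistics of "all vital signs variables in sitting position (raw values and changes from baseline) will be calculated for each visit", together with last and worst on-treatment values, the follow-up visit, and the incidence of potentially clinically significant abnormalities (PCSA). A growth reference appears once, in section 2.1.1, where baseline BMI is put into percentile classes "using the World Health Organization (WHO) growth reference 5-19 years".

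**The concern.** The SAP added weight to the protocol's definition of vital signs but not height. If it is followed as written, a declared safety endpoint is collected from children through the extension and no table, plot or listing of it is specified.

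Weight is tabulated, but as kilograms and change in kilograms. Patients aged 8 to 17 gain weight by growing, at rates that depend on age, sex and puberty. Results are shown by dose group within cohort, and dose groups are defined by body weight below 50 kg or from 50 kg up. Dose group is therefore tied to body size by design, and so plausibly to age and pubertal stage. Groups can differ in weight change with no drug effect. Safety and tolerability is the first secondary objective, and the extension is the only long follow-up this study offers.

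**Working it through.** **1. Where height is collected.** From the flow charts in protocol sections 1.3 and 1.4:
- Cohorts 1 to 3: screening, Visit 8, Visits 12, 14, 16 and 18, and end of extension: 1 + 1 + 4 + 1 = 7.
- Cohort 4: screening, Week 12, Week 36 and Week 48: 4.

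These are scheduled maxima. For a first patient in Cohort 1 enrolled on 29-Sep-2016 (SAP 1.5), Visit 18 at Week 112 falls on 22-Nov-2018, just inside the December 2018 dosing limit. Later patients will have fewer.

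**2. Where height is analysed.**

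| SAP section | Height after baseline |
|---|---|
| 2.1.4 safety endpoints | not named (open list) |
| 2.1.4.4 vital-sign variables | not named (weight, HR, SBP, DBP) |
| 2.4.5 general rule for quantitative parameters | limited to central laboratory or central reading data |
| 2.4.5.4 vital-sign analysis | only the variables of 2.1.4.4 |
| 2.4.5.6 Tanner stages | counts and percentages of stage, not height |
| 2.5.1 conventions | a term in the Schwartz eGFR formula |
| 1.5 and 1.6 change tables | no decision to drop height |

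Baseline BMI (2.1.1) uses height implicitly. Post-baseline height summaries specified: 0.

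**3. Length of follow-up.** Protocol 6.2.1 gives a maximum of about 24 months for the first patients of Cohorts 1 to 3 and about 7 months for Cohort 4. Taking a month as 30.4375 days:
- Cohorts 1 and 2: 29-Sep-2016 + 16 weeks = 19-Jan-2017. To 1 to 31 December 2018 is 681 to 711 days, or 22.4 to 23.4 months of extension. This agrees with about 24.
- Cohort 4: the planned first enrolment is 01-May-2018. To 1 to 31 December 2018 is 7.0 to 8.0 months from Week 0. Of this, 4.3 to 5.3 months follow Week 12. The stated 7 months matches the count from Week 0.

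**4. Why raw weight change is hard to read.** About 10 patients per cohort, with at least 4 in each weight category, gives dose groups of 4 to 6. If one patient's normal weight gain differs by d kg from that of the patient who might have been enrolled instead, the group mean moves by d/6 to d/4. The documents give no growth rates, so d is left unspecified.

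**5. What a standardised summary could deliver.** The documents give no SD for change in a height score. Assume 0.3, range 0.2 to 0.5. The 95% half-width for a mean change is t(0.975, n−1) × SD / √n.

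| n | SD 0.2 | SD 0.3 | SD 0.5 |
|---|---|---|---|
| 30 (Cohorts 1 to 3 pooled, as planned) | 0.07 | 0.11 | 0.19 |
| 10 (one cohort) | 0.14 | 0.21 | 0.36 |
| 5 (one dose group) | 0.25 | 0.37 | 0.62 |

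These assume that every patient contributes, which is optimistic late in the extension. Pooled figures would be usable as description; dose-group figures would be imprecise.

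**The case against.** The strongest reply is that this is a small, uncontrolled dose-finding study with descriptive safety analyses, and that development is already covered by Tanner stage. Protocol 10.5 commits the sponsor to report all safety observations in the study report, SAP 2.1.4 is an open list, and height does feed eGFR and baseline BMI. On that view the remedy is a one-line alignment, and standardised scores are a preference.

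Parts of this stand. A reader might infer that the height data will be wholly unused or never reported. The eGFR and BMI uses and the general reporting commitment do not support that. What is missing is a planned summary, and a general promise to report does not supply one. A reader might also infer that weight is given only as raw change, but raw, last and worst values and PCSA incidence are planned too. The paediatric PCSA criteria are in an appendix not available here, so a weight criterion can be neither confirmed nor excluded.

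A reader might expect the mean standardised score to stay at zero change absent a drug effect. The entry criteria argue against assuming this: patients aged 8 to 9 must be at Tanner stage 1 and those aged 10 to 17 at stage 2 or above, so the sample need not mature like the reference population.

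Finally, one change-from-baseline table over the whole follow-up would cut across the SAP's separate analyses before and after the switch to Phase 3 doses (sections 2.4 and 2.4.5). The fix has to respect that.

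The descriptive nature of the study does not excuse the gap. All safety analyses here are descriptive, and the other declared safety endpoints each have one.

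**Conclusion.** The point holds as a mismatch between protocol and SAP, with a weakness in how weight is summarised. A declared safety endpoint, scheduled up to 7 times in Cohorts 1 to 3 and 4 times in Cohort 4, has no planned post-baseline summary. Weight has no age- and sex-standardised summary. As planned, the outputs will not describe growth.

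It would go too far to say that the extension cannot show whether growth is affected because of the SAP. The data are collected, so the analysis gap can be closed. Without a concurrent control and with about 40 patients, even a good growth analysis would describe and not attribute. Nor is this two years for everyone: about 24 months is a maximum for the first patients of Cohorts 1 to 3. The documents also do not say that the hormone panel was included because of concern about growth, so the point does not rest on that.

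Neither the primary objective nor the efficacy basis for dose selection is affected. The conclusion depends on no assumed number; the SD range above only indicates the precision to expect after the change.

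**What to change.** Add height to SAP sections 2.1.4, 2.1.4.4 and 2.4.5.4. Use the SAP's existing baseline rule, the last value up to the first injection, which for height will normally be the screening value.

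Alongside raw values, report age- and sex-standardised scores for height and BMI, and for weight where the reference covers the patient's age, from the WHO 5-19 years reference already cited. State how ages outside its range are handled.

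Give change from baseline by time point, by cohort and pooled, for the combined main and extension period. For Cohorts 1 to 3 keep the split before and after the switch to Phase 3 doses. Use individual plots or listings where numbers are small. Add a sentence that the result is descriptive and uncontrolled, and that zero expected change in the scores is not assumed because entry criteria select on Tanner stage.

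If the sponsor prefers not to analyse height, section 1.6 should record that decision and the reason.

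The cost is SAP wording and one or two extra tables, with no new measurements.
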